9.2 Toxicity tables/criteria to be used

Toxicity will be assessed according to the NCI Common Terminology Criteria for Adverse Events (CTCAE) version 3.0 (Publish date August 9, 2006). A copy of the Common Terminology Criteria for Adverse Events version 3.0 can be downloaded from http://ctep.cancer.gov/reporting/ctc_v30.html.

9.2.17 Definition of Adverse Event (AE)

An AE “is any unfavorable and unintended diagnosis, symptom, sign (including an abnormal laboratory finding), syndrome or disease which either occurs during the study, having been absent at baseline, or, if present at baseline, appears to worsen.” An AE is a term that is a unique representation of a specific event used for medical documentation and scientific analyses.

9.2.18 Severity of Adverse events

Grade refers to the severity of the AE. The CTCAE v3.0 displays Grades 1 through 5 with unique clinical descriptions of severity for each AE based on this general guideline:

- Grade 1 Mild AE
- Grade 2 Moderate AE
- Grade 3 Severe AE
- Grade 4 Life-threatening or disabling AE (SAE)
- Grade 5 Death related to AE (SAE)

Assessment	Definition
1 = Mild	Discomfort noted, but no disruption of normal daily activities; slightly bothersome; relieved with or without symptomatic treatment
2 = Moderate	Discomfort sufficient to reduce or affect normal daily activity to some degree; bothersome; interferes with activities, only partially relieved with symptomatic treatment.
3 = Severe	Discomfort sufficient to reduce or affect normal daily activity considerably; prevents regular activities; not relieved with symptomatic treatment.

9.2.19 Definition of Serious Adverse Event (SAE)

A serious adverse event is any untoward medical occurrence or effect at any dose, that:

- results in death,
- is life threatening,
- results in persistent or significant disability/incapacity,
- requires in-patient hospitalization[‡] or prolongation of existing hospitalization,
- results in cancer,
- is a congenital anomaly/birth defect in the offspring of a study subject,
- is deemed, by the investigator, an important or serious medical event that may jeopardize the patient or may require intervention to prevent one of the other outcomes listed above should be considered serious (i.e., intensive treatment in an emergency room or at home for allergic bronchospasm; blood dyscrasias or convulsions that do not result in hospitalization; or development of drug dependency or drug abuse.)

9.2.20 Assessment of causality

Every effort should be made by the investigator to explain each adverse event and assess its causal relationship, if any, to the study medication. The degree of certainty with which an adverse event can be attributed to the study medication (or alternative causes, e.g. natural history of the underlying diseases, concomitant therapy, etc.) will be determined by how well the event can be understood in terms of one or more of the following:

- Reaction of similar nature having previously been observed with this type of medication.
- The event having often been reported in literature for similar types of medication.
- Subject’s underlying clinical state or other medical conditions
- Concomitant agents and/or therapies

The causal relationship, if any, to study medication will be defined by one of the following terms:

Assessment	Definition
Definitely	There is suspicion of a relationship between study medication and AE (without determining the extent of probability); there are no other more likely causes and study medication is suspected to have contributed to the AE
Probable	AE cannot be reasonably explained by other factors (i.e. clinical condition, environmental/toxic factors or other treatments)
Possible	AE can be reasonably explained by other factors (as mentioned above)
Unlikely	AE occurs within an unusual time frame of administration of study medication and can also be reasonably explained by other factors (as mentioned above)
Unrelated	There is no suspicion that there is a relationship between study medication and adverse event, there are other more likely causes and study medication is not suspected to have contributed to the AE

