9.1.16 Monitoring of adverse events

The patient will be instructed to contact the investigator immediately should the patient manifest any sign or symptom perceived as serious during the period extending from performance of the first study procedure (e.g. drawing of a blood sample) up to and including 1 month after the last dose (telephone interview at month 25). After this period of time, the patient should report to the investigator only adverse events that are serious and perceived as possibly related to their participation in this study.

Additionally, the patient will be instructed to contact the investigator immediately if he/she believes that he/she has fathered/conceived a child. Testing would be performed to verify that the subject or subject's partner was pregnant. If the pregnancy test were positive, the patient would be instructed to immediately stop taking the study drug and his/her treatment assignment would be revealed to the investigators and the DSMB. The patient or partner would be counseled and followed closely during the pregnancy by the NIH research team and would implement any recommendations made by the DSMB.

Patients will be physically examined by the investigator approximately every 6 months for the study duration. Extensive laboratory monitoring of the following will occur every 6 months for the study duration: CBC with differential, Chemistry panel 20, and urinalysis and pregnancy test (for females with childbearing potential). Additionally, laboratory monitoring (CBC, chemistry panel with liver function tests) will be performed every 3 months after initiation of dosing of idebenone for the first year of treatment and every 6 months thereafter.

All adverse events occurring within 1 month following the last administration of the study medication must be recorded on the Adverse Event Form irrespective of severity and seriousness, and whether or not they are considered related to the study medication. Additionally, all serious adverse events (SAE) brought to the attention of the investigator during the period starting from the day of performance of the first study procedure to the telephone interview on month 25, must be recorded and reported to the FDA in accordance with federal regulations and NIH procedures. Any SAE reported by the patient after month 24, will be subjected to expedited reporting only if judged to be related to the study treatment by the Investigator.

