14.2 Adverse events

All Adverse Events (AEs) will be coded using the Medical Dictionary for Regulatory Activities (MedDRA). The treatment-emergent AEs (i.e., events which start or worsen during the study treatment) will be tabulated by treatment group (when applicable), system organ class and preferred term. Both subject counts (number of patients reporting the event at least once) and event counts (total number of reported events) will be calculated. The percentages out of all patients will be calculated for the subject counts. In addition, incidence rates will be calculated by dividing the event count by patient years of exposure to the study treatment (double-blind phase) or by duration of follow-up (pre-treatment baseline phase).

In addition, the treatment-emergent AEs will be evaluated by severity grade and by relationship to the study treatment. The serious AEs will also be summarized.

15 Execution of statistical analyses

NINDS will be responsible for the final statistical analyses. Santhera Pharmaceuticals may support in conduction of the analyses, but in this case analyses have to be approved by the NINDS.

16 Changes in the planned analyses

This SAP defines the analyses planned in the protocol in more detail and introduces additional sensitivity analyses of the primary endpoint. In addition, the analyses of the secondary efficacy endpoints and safety data have been defined in more detail.

The following minor change was done for the analysis of the primary endpoint. The AUC values will be scaled to the duration of the assessment period, instead of using the calculated AUC values as such (and by dividing the double-blind period AUC values by 4). This change was done prior to unblinding of the study and was deemed as minor and not requiring a protocol amendment.

17 Hardware and software

Statistical analysis, tables and patient data listings will be performed with SAS[®] version 9.4 for Windows (SAS Institute Inc., Cary, NC, USA).

18 References

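### The adverse-event causality terms overlap and 'Definitely' has a weaker test than 'Probable', so the by-relationship table and relatedness-based decisions rest on grades that are not unique

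*Protocol*

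**What the plan says.** Protocol section 9.2.20 asks the investigator to assign each adverse event one of five terms, and says the purpose is to grade how certainly the event can be attributed to study medication. The definitions are:

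- *Definitely* has two parts. It opens with "There is suspicion of a relationship between study medication and AE (without determining the extent of probability"; the second part, which narrows the first, is "there are no other more likely causes and study medication is suspected to have contributed to the AE".
- For *Probable*, the condition is "AE cannot be reasonably explained by other factors (i.e. clinical condition, environmental/toxic factors or other treatments", with no requirement placed on the drug.
- For *Possible*, that condition is turned round to "AE can be reasonably explained by other factors (as mentioned above", again with no requirement placed on the drug.
- For *Unlikely*, a timing element is brought in: "AE occurs within an unusual time frame of administration of study medication and can also be reasonably explained by other factors".
- The bottom term, *Unrelated*, reads in its main part "There is no suspicion that there is a relationship between study medication and adverse event, there are other more likely causes".

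SAP 14.2 first tabulates treatment-emergent events by treatment group, system organ class and preferred term. It then adds that "the treatment-emergent AEs will be evaluated by severity grade and by relationship to the study treatment". It does not say which of the five terms count as related.

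Protocol section 9.1.16 uses the judgement for one reporting decision: a serious event that the patient reports after month 24 "will be subjected to expedited reporting only if judged to be related to the study treatment by the Investigator".

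SAP 4.1 lists the primary safety endpoints as premature discontinuations of treatment, serious adverse events and all adverse events. Relatedness is not part of that definition.

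**The concern.** A causality scale is useful only if a higher term means stronger attribution and each event has one correct term. Here the top term explicitly declines to judge probability, although the section says the scale grades certainty, and the term below it has the harder test. *Possible* is defined only by the existence of another explanation and has no condition on the drug side. Two careful raters applying the table as written could therefore give the same event different grades, and neither would be wrong.

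The first output at stake is the by-relationship table in SAP 14.2, where a higher row would not reliably mean stronger attribution. The second is any decision that turns on relatedness. These include the post-month-24 reporting rule, the relatedness determination for serious events in Protocol section 18, and the monitoring board's option to request unblinding, which under the study-stopping criteria depends partly on an event's potential relationship to the drug. Safety is the first of the trial's primary goals, so a planned safety table should be readable.

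**Working it through.** No arithmetic on trial data applies. The check is to set the five definitions side by side and test order and overlap, then trace where the grade is used.

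| Term | Drug-side condition | Condition on other causes | Timing condition |
|---|---|---|---|
| *Definitely* | drug suspected, probability not judged | none more likely | none |
| *Probable* | none stated | none that reasonably explains the event | none |
| *Possible* | none stated | one that reasonably explains the event | none |
| *Unlikely* | none stated | one that reasonably explains the event | unusual |
| *Unrelated* | no suspicion | others more likely | none |

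**Order.**
1. *Definitely* against *Probable*, on other causes: ruling out a more likely cause still leaves room for an equally likely one. Ruling out any reasonable explanation leaves room for neither. The lower term has the stricter test, so this pair is inverted.
2. *Possible*, *Unlikely*, *Unrelated*: *Unlikely* adds adverse timing to *Possible*, and *Unrelated* removes suspicion altogether. The rank holds from *Possible* down.

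**Overlap.** *Probable* and *Possible* are opposites on a single question, whether something else reasonably explains the event. Between them they cover every event, so the other three terms necessarily fall on top of them:
1. Drug suspected, no reasonable alternative: meets *Definitely* and *Probable*.
2. Drug suspected, equally likely alternative: meets *Definitely* and *Possible*, two levels apart.
3. Any event meeting *Unlikely* also meets *Possible*, because it satisfies the same condition on other causes.
4. Drug not suspected, another cause more likely and reasonable: meets *Possible* and *Unrelated*.

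Five terms give 5 × 4 / 2 = 10 pairs. At least these 4 overlap, and each of the five terms appears in at least one of them.

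**Effect on a two-way split.** Suppose related means *Definitely*, *Probable* or *Possible*. Overlaps 1 and 2 then stay on the related side and disappear when the terms are collapsed. Overlaps 3 and 4 straddle the cut and remain.

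**Where the grade is used.**
- Primary safety endpoints (SAP 4.1): not used.
- Main adverse-event tables (SAP 14.2): not used.
- Recording of adverse events up to one month after the last dose (Protocol 9.1.16): required whether or not the event is thought related.
- Additional by-relationship table (SAP 14.2): used.
- Expedited reporting of serious events reported after month 24 (Protocol 9.1.16): used.

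The documents give no counts of events by causality term, so the number with more than one valid grade cannot be computed.

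**The case against.** The strongest reply is that the damage is small. No primary safety count changes however causality is graded, and the by-relationship summary is an addition to the main tables. The trial is double-blind, so inconsistent grading should not favour an arm. Serious events have safeguards outside this table: relatedness is settled by the principal investigator in consultation, and all serious events go to the monitoring board. All of that stands and sets the limits of the point.

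A second reply is that raters would read the table sensibly. They would take *Unlikely* rather than *Possible* when timing is odd, and would use the considerations listed ahead of the table, such as similar reactions seen before with this type of drug. This has some force for the lower terms. But those considerations are not tied to any term, nothing tells the rater to choose the most specific match, and no such reading repairs the inversion at the top.

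Four stronger readings are tempting, and the documents do not support them:
- A reader might infer that the primary safety endpoint is misclassified. SAP 4.1 defines it without relatedness.
- A reader might infer that *Definitely* needs suspicion alone. Its entry also requires that no other cause be more likely.
- A reader might infer that the whole scale is out of order. The inversion is confined to the top pair.
- A reader might infer that events will be misgraded, and that in this disease the ambiguous case is the usual one. There are no grading data. Where the disease is the more likely cause, *Definitely* fails and that overlap does not arise.

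Finally, Protocol section 7.6.10 says data analysis has been completed, so new definitions cannot alter grades already given. That is correct and shapes the remedy.

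**Conclusion.** The point holds within limits. As written, the causality terms are not mutually exclusive and *Definitely* carries a weaker test than *Probable*. At least four of the ten pairs of terms overlap, and two of those four straddle the natural related/not-related line.

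The consequence is a risk of inconsistent grading in one additional safety table and in decisions that depend on relatedness. Discontinuations, serious events, all adverse events and the main tables by arm are untouched.

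The conclusion rests on reading the definitions literally. The expectation of no difference by arm assumes that the blind held. The size in events is unknown and is not claimed.

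**What to change.** 1. In Protocol 9.2.20, reconcile the five definitions into an ordered, mutually exclusive set in which the top term has the strictest test and *Possible* carries a drug-side criterion. This serves any further grading and any reuse of the scale.
2. In SAP 14.2, or in the study report if the SAP is closed, state which terms count as related.
3. For events already graded, report only the collapsed split: *Definitely*, *Probable* and *Possible* against *Unlikely* and *Unrelated*. Add a footnote that *Possible*, as defined during the trial, overlaps both lower terms, so the cut is itself imprecise.
4. Rest safety conclusions on the all-causality tables by arm, which do not depend on the scale.

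The cost is one definitions table, one sentence in the SAP or report, and one footnote. No new data are needed. For the existing data only items 2 to 4 can still have an effect.

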9.2.21 Treatment of adverse events

Treatment of any AE is at the sole discretion of the investigator and according to current available best treatment. The applied measures will be recorded in the patient's chart.

1.2 Criteria for individual subject withdrawal

A subject *must* permanently discontinue study drug treatment for any of the following reasons:

1. The subject becomes pregnant (pregnancy test will be performed for female patients with child bearing potential during study visits as indicated in section 7.5.6). If a patient becomes pregnant, treatment must be *immediately* discontinued. The pregnancy must be reported to the NIB (treating physician/research nurse) and to the IRB immediately. Information about the subject, the subject's pregnancy, the outcome of the pregnancy, and the status of the infant at 8 to 12 weeks of age will also be collected.
2. The subject desires to discontinue study drug treatment under this protocol. Patients have the right to withdraw from the study at any time and for any reason. The investigator also has the right to withdraw patients from the study in the event of an intercurrent illness, adverse events, treatment failure, protocol violations, administrative reasons, or other reasons.
3. 1st MS safety criterion: Worsening of more than two points on the EDSS scale (*Kurtzke 1983*) compared to baseline, confirmed one month later on an extra follow-up visit. The treatment will be discontinued, but the patient will be followed off therapy to collect all predetermined outcome measures as per "intention to treat" analysis.
4. 2nd MS safety criterion: The average number of new CEL (which represents a measure of MS-related brain inflammatory activity) increases after initiation of idebenone therapy 3 standard deviations above the average number of CEL during pre-treatment baseline or for patients with no CEL observed on MRIs collected during baseline period (expected to be majority of PP-MS patients), the number of CEL recorded on a single follow-up MRI reaches 10 CEL (total). Treatment will be discontinued, but the patient will be followed off therapy to collect all predetermined outcome measures as per "intention to treat" analysis.
5. Laboratory safety criteria: ALT (SGPT) or AST (SGOT) more than three times the upper limit of normal during regular laboratory monitoring and remains more than three times the upper limit after one week of cessation of idebenone dosing. Any other highly abnormal laboratory finding that is deemed critical by an investigator and that persists for 1 week after cessation of drug dosing.

The reasons for discontinuation of the study drug must be recorded in the subject's Clinical Center patient file. Patients discontinuing dosing will be followed for an additional 2 months. If discontinuation was because of an adverse event, the patient will be followed until the event is resolved or stabilized. If the discontinuation was because of pregnancy, the subject will be followed until after the birth.

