7.5 Study procedures

7.5.1 Study visits

Each study visit (Figure 1) and MRIs should occur as indicated. These time points are approximated. To accommodate for patient scheduling needs or clinical necessity, study visits will be accepted within a +/- 4 week window of the timepoints noted. Biological samples (CSF, whole blood, apheresis sample) should be collected within 4 weeks of the MRI examination as indicated in Figure 1. Blood samples at baseline and 1 year of treatment will be collected concomitantly with CSF samples.

7.5.2 Clinical and functional evaluations:

to be performed every 6 months

1. Comprehensive neurological evaluation
2. Expanded Disability Status Scale (EDSS (*Kurtzke 1983*))
3. Scripps Neurological Rating Scale (NRS (*Sharrack and Hughes 1996*))
4. MS Functional Composite Scale (MSFC (*Cutter, Baier et al. 1999*), which consists of 3 functional tests:
 - a. Paced Auditory Single Digit Addition Test (PASAT) – measure of cognitive skills
 - b. Timed 25 foot walk – measure of ambulation
 - c. 9-hole peg test – measure of fine finger motor movements
5. Symbol Digit Modality Test (*Sepulcre, Vanotti et al. 2006*)
6. Extensive evaluation of strength, balance and gait within the context of a physical therapy (PT) evaluation may be performed if the subject is not too disabled to participate in these evaluations safely and reliably. This optional evaluation will be conducted in the Biomechanics Laboratory of the Rehabilitation Medicine Department, NIH, CC. It will include, but may not be limited to, the following:
 - a. Evaluation of strength and tone
 - b. Evaluation of gait
 - c. Balance assessment

The assessment of strength and spasticity may require the use of surface EMG.

7.5.3 Neuroimaging evaluation:

MRI imaging will consist of combined MRI of the brain and upper cervical spinal cord, which will be performed every 6 months. This MRI will focus on quantitative and volumetric analyses of brain structure and tissue integrity. Inflammatory activity is less prominent in PP-MS as compared to RR-

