Consequently, this mathematical analysis confirmed that 2-year AUC must be divided by 4 to obtain equivalent yearly change. The intercept (-0.77) represents improvement in disability, which is incorrectly ignored when the treatment period is split into two yearly AUCs.

Statistical Hypothesis

The hypothesis to be tested for the primary efficacy endpoint CombiWISE is:

H₀: There is no difference between idebenone and placebo in the disability progression during the 2-year treatment period.

The alternative superiority hypothesis is

H_A: The disability progression in idebenone-treated patients is slower than in the placebo-treated patients during the 2-year treatment period.

In addition to the difference between the treatment groups, the within-group changes in each treatment group will be evaluated by comparing the disability progression during the pre-treatment period to the progression during the treatment period.

The analysis for the primary outcome measure CombiWISE will be performed in all randomized patients using a two-sided type I error rate of $\alpha = 0.05$.

Primary Analysis of the Primary Outcome Measure

The AUCs of the CombiWISE scores during the 2-year treatment period will be analyzed using an Analysis of Covariance (ANCOVA) model with the AUC of the pre-treatment CombiWISE scores, Baseline (Month 0) CombiWISE score and Baseline age as covariates.

The incomplete data in the CombiWISE scores during the 2-year treatment period will be managed with the single imputation algorithm defined in Section 5.3.

The within group changes will be tested using paired t-test within each treatment group. For this analysis, to compare the 1-year pre-treatment period changes to 2-year treatment period changes, the treatment period AUC values will be divided by 4.

Sensitivity Analyses of the Primary Outcome Measure

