4.3 Secondary efficacy endpoints

All components of the primary endpoint will be analyzed as secondary endpoints:

- EDSS: the EDSS score (scored as 1.0, 1.5, ..., 10.0) is recorded as such and requires no derivation.

-
- SNRS: the SNRS score, which can range between 100 (normal status) and 0 (worst possible score) is recorded as calculated by the investigator.
 - 25 foot walk (25FW): 25FW is the average of two attempts of walk test. In case any of the two attempts is unsuccessful, 25FW will be set as missing. This endpoint will be primarily analyzed without any transformation to facilitate the interpretation, but in case the data are skewed, additional analyses may be conducted by log2 transformation of the average.
 - 9 hole peg test (9HPT) performed on non-dominant hand (NDH-9HPT): NDH-9HPT is the average of the two attempts on 9 hole peg test. In case any of the two attempts is unsuccessful, NDH-9HPT will be set as missing. This endpoint will be primarily analyzed without any transformation to facilitate the interpretation, but in case the data are skewed, additional analyses may be conducted by log2 transformation of the average. Furthermore, similar analyses will be conducted for data based on the dominant hand and the average of the non-dominant and dominant hands.

In addition, the following variables will be analyzed as secondary endpoints:

- Neuroimaging outcomes: Inhibition of individualized rates of enlargement of ventricular volume: enlargement of segmented volume of lateral and 3rd ventricles. This was the primary endpoint of the initial protocol version.
- EDSS-plus, as defined in (Cadavid, Cohen et al. 2017): EDSS-plus is defined as progression on at least 1 of 3 components (EDSS, 25FW, and/or NDH-9HPT) confirmed ≥ 24 weeks apart and with a $\geq 20\%$ minimum threshold change for 25FW and NDH-9HPT. As the visits in this study are scheduled to be conducted with 6 month intervals, a confirmation at the next scheduled visit is considered sufficient, even if the time between the visits would be less than 24 weeks due to visit scheduling.

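### The 2-month follow-up rule after stopping study drug conflicts with outcome follow-up stated elsewhere, and about 51–67% of the patients it covers would have no further primary-outcome visit

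*Protocol*

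**What the plan says.** Protocol 9.3 (Criteria for individual subject withdrawal, printed as 1.2 in the body) lists five grounds for permanently stopping study drug.

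- **Items 3 and 4** (confirmed EDSS worsening; increase in enhancing lesions). For item 3: "The treatment will be discontinued, but the patient will be followed off therapy to collect all predetermined outcome measures". Item 4 says the same, and both cite intention to treat.
- **Items 1, 2 and 5** (pregnancy; the patient's wish or investigator withdrawal, including for adverse events; laboratory criteria). No outcome collection after stopping is stated. Item 2 begins "The subject desires to discontinue study drug treatment under this protocol" and goes straight on to withdrawal from the study.
- **Closing paragraph**, with no exemption for items 3 and 4: "Patients discontinuing dosing will be followed for an additional 2 months". It then adds: "If discontinuation was because of an adverse event, the patient will be followed until the event is resolved or stabilized". A pregnancy is followed until after the birth. Neither extension mentions an outcome visit.

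Elsewhere, Protocol 7.4 has randomised patients followed for a further 24 months, and Protocol 7.6 ends individual participation at the Month 24 visit. Clinical evaluations are "to be performed every 6 months" (Protocol 7.5.2) and brain MRI has the same interval (7.5.3). SAP 4.2 scores CombiWISE on treatment at Months 6, 12, 18 and 24. Protocol 7.5.1 allows 4 weeks either side.

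On analysis, Protocol 11.2 states: "The analysis for the primary outcome measure CombiWISE will be performed in all randomized patients". SAP section 8 limits ITT to randomised patients with at least one efficacy assessment after Month 0, and the SAP prevails where the two differ. SAP 4.2 sets AUC values after premature discontinuation to missing without defining that term.

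**The concern.** A 2-month tail does not fit a 6-month visit schedule. Read as written, the closing paragraph lets most patients stopping under items 1, 2 and 5 go before their next CombiWISE assessment, while patients stopping under items 3 and 4 stay on the full schedule. Outcome data after stopping are then kept or lost according to the reason for stopping, and that reason may well be related to outcome.

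Three consequences follow.

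- Patients who stop early can leave the ITT set altogether.
- Patients with some post-baseline data stay in the primary analysis, but only on their observed part: SAP 4.2 scales the AUC by the square of the time to the last visit.
- For EDSS-plus, SAP 4.3 says "a confirmation at the next scheduled visit is considered sufficient". A first progression seen at the last visit before stopping will usually have no next visit to confirm it.

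Collecting the visits may also not be enough. SAP 4.1 uses premature discontinuation to refer to study treatment. If SAP 4.2 means the same, off-drug scores collected under items 3 and 4 would be discarded from the primary AUC.

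**Working it through.** **The plan's own attrition figure.** Protocol 11.6 recruits up to 85 to allow for 20% drop-out and end with 66 treated patients. 66 / (1 − 0.20) = 82.5, rounded up to 83, which is close to the stated 85. Protocol 7.1 expects those 66 to finish treatment. The 20% is therefore used in getting from 85 to 66 and is not a discontinuation rate among the 66.

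**Inputs.** Follow-up after stopping: 2 months (Protocol 9.3). Visit spacing: 6 months (Protocol 7.5.2, SAP 4.2). Window: 4 weeks = 28 / (365.25/12) = 0.92 months (Protocol 7.5.1). Assumption, not in the documents: stopping times are uniform over Months 0–24.

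**Chance of one more visit under the 2-month rule.** The next visit is reached only if it falls within 2 months of stopping.

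- Nominal timing: 2/6 = 33% reach it; 67% do not.
- Next visit always moved to the early edge of its window: (2 + 0.92)/6 = 49% reach it; 51% do not.
- Visits scattered at random within the window (simulation): 33% reach it, the same as nominal.

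**Share of later visits lost, nominal timing.** The mean number of visits still scheduled at stopping is (4 + 3 + 2 + 1)/4 = 2.5. The mean number reached is 0.33. Lost: 1 − 0.33/2.5 = 87%.

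**No post-baseline visit at all.** This applies to stops before Month 6 − 2 = 4, or before Month 6 − 2.92 = 3.08 with the earliest possible visit. Under uniform stopping that is 4/24 = 17%, or 3.08/24 = 13%, of those under the rule. They fall outside the SAP's ITT set.

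**Patient numbers, by assumption only.** If 10, 20 or 30% of 66 stopped drug and all came under the 2-month rule, that is 6.6, 13.2 or 19.8 patients. Those with no further visit:

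- nominal timing (× 2/3): 4.4, 8.8 or 13.2;
- earliest visits (× 0.51): 3.4, 6.8 or 10.2.

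Every patient who stops under item 3 or 4 instead lowers these counts.

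**The case against.** The strongest reply is that nobody is released at 2 months. The sentence sits in the subject-monitoring section beside adverse-event and pregnancy follow-up, so it can be read as a safety provision. Sections 7.4 and 7.6 take participation to Month 24, and items 3 and 4 can be read as specific rules overriding the general one. This reading is possible. But the closing paragraph does not say it, and if every patient stayed to Month 24 regardless, items 3 and 4 would need no outcome clause of their own. The request to reconcile the passages stands on either reading.

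Second, the SAP plans multiple imputation under missing at random and under a copy-reference assumption (13.1.2). These mitigate the loss, but they are sensitivity analyses. With few off-drug visits, the missing-at-random version models off-drug patients largely from on-drug patients in the same arm. Neither version replaces the data.

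Third, a reader might infer that losses fall mainly on idebenone through gastrointestinal intolerance. The documents do not settle this. Protocol 4.5 reports such symptoms more often on idebenone in Alzheimer's trials. Protocol 9.1 reports similar event frequencies on placebo across double-blind trials. Protocol 4.5 also describes a 12-month Huntington's disease trial, at a lower dose, in which nobody left for an adverse event attributed to the drug. Nor is it right that all worsening patients are kept: item 3 requires confirmed worsening of more than two EDSS points, and treatment failure sits in item 2 with no outcome follow-up.

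**Conclusion.** The protocol contradicts itself on follow-up after stopping study drug and is silent on outcome collection for items 1, 2 and 5. Under the 2-month rule as written, about 51–67% of the patients it covers would have no further CombiWISE visit, and stops before about Month 3–4 would leave no post-baseline visit. The percentages rest on stops being spread evenly between visits. Bias from retention that depends on the reason for stopping is a real possibility; its direction and any imbalance by arm are not established.

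Three stronger readings should be avoided.

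- The rule cannot be applied to everyone who stops drug, because items 3 and 4 require full outcome collection.
- A reader might take 20% of 66 (13 patients), assume two lost visits each, and arrive at 26 of 264 visits (10%). The 20% is an accrual allowance already spent, and the documents give no discontinuation rate among the 66.
- The rule does not defeat a governing promise to analyse everyone randomised. That wording is the protocol's; the SAP, which prevails, requires one post-baseline assessment.

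**What to change.** Reconcile Protocol 7.4, 7.6 and 9.3 so that the outcome-collection wording of items 3 and 4 applies to every reason for stopping study drug. Patients who do not withdraw consent to follow-up stay on the scheduled Month 6, 12, 18 and 24 outcome assessments, with MRI subject to the protocol's existing pregnancy safeguards. Leave the safety follow-up and the drug-stopping rules as they are.

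State in SAP 4.2 that premature discontinuation means leaving the study, not stopping drug, so that off-drug scores enter the primary AUC. Without this, the added visits might never be used.

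The cost is mainly wording, because the visits are already scheduled for every randomised patient. The small downside is that some patients off drug must keep attending, and some will decline.

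Protocol 7.6 records that data analysis is complete, so rewording cannot recover visits in this trial. For the completed trial, report by arm and by reason how many patients stopped drug and how many later outcome visits were obtained. That would show whether the loss was small or large, and whether it was balanced.
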